## **6 FOLLOW UP AND OUTCOME EVALUATION**

### **6.1 Follow-Up Schedule**

All participants will be followed every 2 weeks during the intervention. At each visit, patient's performance status and toxicity of treatment will be monitored, and blood test will be checked for complete blood count, liver function, and renal function. Thyroid function test and early morning cortisol (9am) will be performed at least every 4 weeks while on bintrafusp alfa therapy. For female patients in reproductive age, urine or serum pregnancy test needs to be performed at least every month while the subject is on bintrafusp alfa therapy. All adverse events and laboratory abnormalities will be graded per the National Cancer Institute Common Terminology Criteria for Adverse Events, version 4.0.

For blood-borne immune markers and exploratory biomarkers, plasma EBV DNA will be determined before treatment and every 2 weeks until disease progression; plasma TGF $\beta$ 1 measurement will be performed every 8 weeks until disease progression; exo-PD-L1 concentration will be measured every 2 weeks until disease progression.

Tumor imaging by CT head, neck, chest, abdomen, and pelvis will be done at baseline, every 8 weeks for the first 12 months, then every 12 weeks thereafter. Response will be assessed per RECIST version 1.1. Treatment decisions will be based on Investigator(s) review.

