## 6.2 Outcome Measures

Primary outcome:

- Objective response rate (ORR): The percentage of patients with radiologically complete or partial response as determined by the Investigator according to RECIST version 1.1.

Secondary outcomes:

- Progression-free Survival (PFS): PFS is measured from the date of informed consent to radiographically documented progression according to RECIST 1.1 or death from any cause (whichever occurs first). Participants alive and without disease progression or lost to follow-up will be censored at the date of their last radiographic assessment
- Time to progression (TTP): TTP is measured from the date of informed consent to radiographically documented progression according to RECIST 1.1. Participants death and without disease progression, alive without disease progression, or lost to follow-up will be censored at the date of their last radiographic assessment
- Overall survival (OS): OS is measured from date of informed consent to the date of death from any cause. Participants alive or lost to follow-up will be censored at the date of their last radiographic assessment

Survival rate at 12 months and 24 months: The percentage of study population who are still alive for 12 months and 24 months from the date of study enrollment. Participants alive or lost to follow-up will be censored at the date of their last radiographic assessment

Duration of response (DOR): DOR is the time from documentation of tumor response to radiographically documented disease progression

- ORR, TTP, and PFS of the same definitions as above are measured against immune-related RECIST (irRECIST) criteria as one of the secondary endpoints.
- Safety outcome measures: Incidence, nature, and severity of adverse events graded according to the National Cancer Institute Common Terminology Criteria for Adverse Events (NCI-CTCAE v.4)
- Pre-treatment, serial post-treatment plasma EBV-DNA levels, and dynamics of

EBV DNA levels will be measured

- Disease control rate (DCR): The percentage of patients with a CR, PR, or SD  $\geq$  6 months per RECIST 1.1
- Time to response (TTR): TTR is measured from the date of informed consent to first radiographically documented tumor response per RECIST 1.1
- Quality of life (QoL): as assessed by the European Organization for Research and Treatment of Cancer Core Quality of Life Questionnaire (EORTC-QLQ-C30) and the head and neck cancer-specific H&N-35 questionnaires

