### **6.3 Follow-Up and Record of Events**

- The patients should be followed-up for up to 2 years.
- The incidence of late toxicities  $>$  grade 3 by Common Toxicity Criteria for Adverse Events version 4.0 (NCI-CTCAE v.4) should be recorded.
- All causes of death (if occur) will be recorded. Deaths due to unknown cause are counted as deaths due to NPC if disease is still present at last assessment.

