### **6.4 Criteria for Removal from Protocol Treatment**

- Disease progression
- Inter-current disease that would affect assessments of clinical status to a significant degree, require discontinuation of drug, or both.
- Unacceptable toxicity.
- The patient may withdraw from treatment at any time for any reason. The reason should be recorded. Follow-up will be continued for all consenting patients for up to 2 years.

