## 7 STATISTICS

### 7.1 Statistical Analysis

Objective response rate (ORR) will be expressed based on exact binomial distribution. Survival outcomes, including TTP, PFS, OS, and survival rate their corresponding 95% confidence interval, will be estimated using Kaplan-Meier method. The Fisher exact test will be used to correlate the binary clinical and biomarker data. The cut-off values of baseline and changes in the exo-PD-L1 and TGF- $\beta$ 1 levels will be calculated by the Receiver Operating Characteristic (ROC) curve analyses.

All of the reported P values will be 2-tailed, and P<0.05 will be considered statistically significant. No multiplicity will be considered. The analyses will be performed using statistical software packages SPSS and R.

**Procedures for Handling Missing, Unused, and Spurious Data:** All available data will be included in the data listings and tabulations. Where appropriate, imputations of values for missing data for primary and secondary efficacy analyses will be performed as specified in the Statistical Analysis Plan. All data recorded on the CRF will be included in the data listings that will accompany the clinical study report.

If, after the study has begun, but prior to the conduct of any analysis, changes made to primary and / or key secondary endpoints, or the statistical methods related to those hypotheses, then the protocol will be amended. Changes to exploratory analyses made after the protocol finalized will be documented and referenced in the final report. Post hoc exploratory analyses will also be identified in the final report.

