- f. Hematology parameters include the following laboratory tests: complete blood count with 3-part differential (i.e. total neutrophil count including bands, lymphocytes, and monocytes), hemoglobin, hematocrit and platelets.
- g. Blood chemistry must include glucose, BUN, creatinine (eGFR), sodium, potassium, magnesium, chloride, calcium, CO2, alkaline phosphate, AST (SGOT), total bilirubin, total protein, albumin, phosphorus, uric acid.
- h. Coagulation test include PT, PTT and INR.
- i. Plasma EBV DNA will be determined before treatment and every 2 weeks until disease progression; plasma TGF $\beta$ 1 measurement will be performed every 8 weeks until disease progression; PD-L1 concentration in the exosome will be measured every 2 weeks until disease progression.
- j. Pregnancy test will be performed within 1 week prior to treatment, if a cycle is missed during treatment or pregnancy and at the end of treatment visit only for women of childbearing potential.
- k. Patients will have CT scan at Screening/Baseline ( $\leq$  28 days prior to initiation of trial treatment), every 8 weeks for the first 12 months, and every 12 weeks thereafter. Patients will also have CT scan whenever disease progression is suspected. For patients who discontinue treatment without radiographic progression per RECIST 1.1 (e.g. in patients who discontinue treatment for clinical progression or adverse reactions), disease assessment should continue as stated in schedule until radiographic disease progression or alternate therapy is given.
- l. Quality of life (QoL) will be assessed by patient-reported EORTC QLQ-C30 and H&N-35 questionnaires every 12 weeks in the first year.
- m. If screening assessments were completed within 28 days, they do not need to be repeated on Day 1 of Cycle 1 if patient's condition has not changed.

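### Overall survival censors living patients at their last scan but counts every later death, so survival is biased downward and the 24-month rate falls towards zero

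*Protocol*

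**What the plan says.** Section 6.2 defines OS from informed consent to "date of death from any cause. Participants alive or lost to follow-up will be censored at the date of their last radiographic assessment". The same censoring sentence follows the survival-rate outcome, defined as "The percentage of study population who are still alive for 12 months and 24 months from the date of study enrollment". It also appears, appropriately, under PFS and TTP. Section 7.1 fixes the estimator: "Survival outcomes, including TTP, PFS, OS, and survival rate their corresponding 95% confidence interval, will be estimated using Kaplan-Meier method".

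Scans and vital status run on different clocks:

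- Section 6.1 schedules CT "every 8 weeks for the first 12 months, then every 12 weeks thereafter".
- Appendix 11, footnote k, says that for patients who leave treatment without radiographic progression "disease assessment should continue as stated in schedule until radiographic disease progression or alternate therapy is given".
- Section 6.4 lists "Disease progression" first among the reasons for removal from treatment.
- Section 6.3 says "The patients should be followed-up for up to 2 years" and requires all deaths to be recorded. Section 6.4 continues follow-up over the same period for consenting patients who withdraw.

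Nothing in the protocol gives OS a censoring date based on when the patient was last known to be alive.

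**The concern.** The rule suits an endpoint that is only seen on scans. For OS it makes the length of observation depend on the outcome. Take two patients who progress at month 4. One dies at month 14 and counts as an event at month 14, having been at risk for 14 months. The other is alive at month 24 and is censored at about month 4. Kaplan-Meier assumes that patients censored at a given time have the same prospects as those who stay under observation. Here, those who stay after their last scan are exactly those who go on to die.

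Median survival, OS and the 12- and 24-month rates are named secondary objectives (Section 2.2). The trial has a single arm, so its survival figures are likely to be read against published rates such as those in the background. A 24-month rate near zero would reflect the censoring rule and not the drug, and it would discard survival follow-up that patients had provided.

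**Working it through.** The protocol gives no OS figure to reproduce. Its response-rate design (stop at 4 or fewer of 18, succeed at 11 or more of 33) has exact type I error 0.0458 and power 0.8011, as stated, and this point does not touch it.

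**Inputs from the protocol**

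- Scenario A, nivolumab study in Section 1: 12-month PFS 19.3%, 12-month OS 59%.
- Scenario B, pembrolizumab study in Section 1: 12-month PFS 30.1%, 12-month OS 66.7%.
- CT every 8 weeks to month 12, then every 12 weeks; follow-up 2 years.

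**Assumptions not in the protocol**

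- Exponential times to progression and from progression to death.
- A fraction f = 10% of PFS events are deaths (30% in sensitivity runs).
- 14 days from consent to first dose (0 and 28 in sensitivity runs).
- CT at weeks 8, 16, ..., 48, then 60, 72, 84, 96, ending at the scan that shows progression.

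**Calibration.** With PFS hazard λ and post-progression hazard μ per month,

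S(t) = e^(−λt) + (1 − f) · λ · (e^(−μt) − e^(−λt)) / (λ − μ).

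Scenario A: λ = −ln(0.193)/12 = 0.1371. Solving S(12) = 0.59 gives μ = 0.0850. Check: 0.193 + 0.9 × 0.1371/0.0521 × (0.361 − 0.193) = 0.59. The true 24-month OS is then S(24) = 0.257. Scenario B: λ = 0.1001, μ = 0.0808, S(24) = 0.340.

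**Large-sample Kaplan-Meier, 24 months of follow-up for all**

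| Month | A, protocol rule | A, last known alive | B, protocol rule | B, last known alive |
|---|---|---|---|---|
| 12 | 0.55 | 0.59 | 0.64 | 0.67 |
| 18 | 0.30 | 0.40 | 0.41 | 0.48 |
| 22 | 0.15 | 0.30 | 0.26 | 0.38 |
| 24 | 0.00 | 0.26 | 0.00 | 0.34 |
| Median, months | 13.2 | 14.6 | 15.6 | 17.5 |

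The median censoring time of patients who are in fact alive at month 24 is 11.5 months in A and 17.0 in B. With follow-up spread evenly over 12 to 24 months, A gives 12-month OS 0.51 and a median of 12.2 months.

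**Why month 24 collapses.** The last scan before month 24 is at week 96, or 0.46 + 96/4.348 = 22.5 months from consent. Every survivor has been censored by then. Those still at risk after month 22.5 all die before month 24, so the product-limit estimate reaches zero.

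**At trial size.** The estimate is zero whenever the last observation is a death. One death between months 22.5 and 24 is enough. In A, S(22.54) − S(24) = 0.286 − 0.257 = 0.029 per patient, so with 33 patients the chance of at least one is 1 − 0.971^33 ≈ 0.62 to 0.63. When CT ends at progression, many censoring times are earlier and the chance is a little higher. Simulated trials of 33 give an estimate of exactly zero in about two thirds, with median 0.00 and mean about 0.04 (A) or 0.07 (B).

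**Sensitivity, follow-up ending 24 months from consent.** Across 0 to 28 days' screening, CT grids with and without a week-104 scan, and f of 10% or 30%, the large-sample 24-month value is 0.00 in every run. With 33 patients the estimate is exactly zero in 44% to 84% of trials. With f = 30% the 12-month values are about 0.53 against 0.59 (A) and 0.62 against 0.67 (B).

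**The case against.** **That CT ends at progression is partly inferred.** Footnote k speaks of patients who stop treatment without progression, Section 6.1 names no stopping point, and the immune-related RECIST endpoints suggest some scans after RECIST 1.1 progression. This is fair, and it matters for part of the size. If CT continues on schedule until death or month 24, the 12-month rate and median are essentially correct under full 2-year follow-up (A: 0.59 and 14.6 months). The 24-month value is still 0.00 in both scenarios, and exactly zero in roughly 63% to 66% of trials of 33, because the last scan still precedes month 24.

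**The collapse depends on when follow-up ends.** This also stands. Section 6.3 gives no starting point for the 2 years. If they run from first dose and a scan falls at week 104, the 24-month value is 0.10 to 0.12 against 0.26 to 0.34 (A) and 0.20 to 0.23 against 0.34 to 0.42 (B). With vital status to 24–36 months it is 0.16 against 0.26 and 0.25 against 0.34; to 24–48 months, 0.20 against 0.26 and 0.29 against 0.34. These cases need a favourable scan date or more follow-up than the protocol states, and each remains too low.

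**The earlier effects are small beside the trial's precision.** A 12-month bias of 3 to 4 points compares with a simple 95% half-width of 1.96 × √(0.59 × 0.41/38) ≈ 16 points. True, but the bias is systematic and avoidable, and this does not apply at 24 months.

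**OS is secondary and the error is conservative.** The go/no-go decision rests on response rate alone, and the error cannot create a false claim of efficacy. That limits the harm but does not make the survival estimates usable.

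**Conclusion.** The concern holds. Under the stated rule, remaining at risk after the last scan depends on dying later, so OS and both survival rates are biased downward. The direction follows from the rule and needs no simulation.

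The size depends on timing. At 12 months the loss is about 3 to 4 points (5 to 6.5 if 30% of PFS events are deaths), and the median falls by 1.4 months in A and 1.9 in B, provided CT ends at progression. At 24 months, with follow-up ending 2 years from consent, the large-sample estimate is zero where the truth in these scenarios is 26% to 34%, whether or not CT continues past progression. If a scan falls at about month 24 or vital status is followed longer, the shortfall is about 5 to 23 points.

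The figures rest on exponential times and on background rates from other drugs, so they are illustrations and not predictions. The primary response-rate analysis is unaffected. Because a named secondary endpoint cannot be estimated validly as written, this should be corrected before analysis.

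**What to change.** In Section 6.2, replace the censoring sentence in the two places where it governs survival (OS, and the 12- and 24-month rates) with: *Participants not known to have died will be censored at the date they were last known to be alive.* Keep censoring at the last radiographic assessment for PFS and TTP. In the simulation this change recovers the true values (12 and 24 months: 0.59 and 0.26 in A; 0.67 and 0.34 in B).

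The cost is two sentences. The appendix already has a survival follow-up row, and Sections 6.3 and 6.4 already provide for up to 2 years of follow-up. Confirm that contacts after progression record a last-known-alive date: the last mark in that row appears to fall in the disease-progression column, and no later contact interval is shown. If the date is not already captured, add one line requiring it. State as well the date from which the 2 years run, so that vital status at month 24 is obtained for every patient. No additional scans are needed.

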### **2.2 Secondary Objectives**

1. To assess the progression-free survival (PFS) per RECIST version 1.1
2. To assess the time-to-progression (TTP) per RECIST version 1.1
3. To assess the median survival, overall survival (OS) and survival rate in 12 months and 24 months
4. To evaluate the disease control rate (DCR), duration of response (DOR), and time to response (TTR) in previously treated R/M NPC patients receiving bintrafusp alfa
5. To measure the toxicities and tolerability in previously treated R/M NPC patients receiving bintrafusp alfa
6. To investigate the relationship between the response to bintrafusp alfa and plasma Epstein-Barr virus (EBV) deoxyribonucleic acid (DNA) level
7. To evaluate ORR, PFS and TTP, OS, and DCR per immune-related RECIST (irRECIST)
8. To evaluate the patient-reported quality of life (QoL) during treatment

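### Duration of response ends only at radiographic progression; if a responder dies without documented progression and is censored, it may be overstated and will disagree with PFS for that patient

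*Protocol*

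**What the plan says.** DOR is part of the fourth secondary objective in protocol section 2.2: "To evaluate the disease control rate (DCR), duration of response (DOR), and time to response (TTR"). Section 6.2 defines it in one sentence: "DOR is the time from documentation of tumor response to radiographically documented disease progression". That sentence does not mention death and gives no censoring rule.

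Two neighbouring definitions in section 6.2 do deal with death, in opposite ways:

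- PFS ends at "radiographically documented progression according to RECIST 1.1 or death from any cause (whichever occurs first"). Patients alive without progression are censored at their last radiographic assessment.
- TTP ends at radiographic progression only, and the rule for death is written out: "Participants death and without disease progression, alive without disease progression, or lost to follow-up will be censored" at the last radiographic assessment.

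No other part of the protocol adds death to DOR. Section 7.1 says "Survival outcomes, including TTP, PFS, OS, and survival rate their corresponding 95% confidence interval, will be estimated using Kaplan-Meier method", which does not name DOR. Section 6.3 says "All causes of death (if occur) will be recorded", so the information needed to count death is collected.

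**The concern.** DOR describes how long responses last. A response has ended when the patient dies, whether or not a scan showed progression first. Under the stated definition such a patient never reaches the end of response. If the patient is censored, the analysis treats the response as one that could have continued like those of the responders still being followed. The censoring is then informative, because death is unlikely to be unrelated to the state of the disease.

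The gap can arise in practice. CT is every 8 weeks for 12 months and every 12 weeks after that (section 6.1), so a patient may die between scans. After treatment stops without progression, "disease assessment should continue as stated in schedule until radiographic disease progression or alternate therapy is given" (Appendix, schedule of assessments), so a death after a change of therapy may have no progression scan before it.

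At stake is the description of durability in a single-arm trial whose primary endpoint is the response rate. A progression-only TTP does little harm because PFS stands next to it. DOR has no such companion, so readers would see only the version that leaves death out.

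**Working it through.** **No DOR figure to reproduce.** The protocol states no expected median, rate or precision for DOR. The check is a comparison of definitions, then an illustration of size.

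**One patient under each definition (hypothetical).** First response at the week 8 scan, no progression at the week 16 scan, death at week 20.

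| Endpoint | What happens to this patient |
|---|---|
| PFS (section 6.2) | Event at death, week 20 |
| TTP (section 6.2) | Censored at the last scan, week 16 |
| DOR as written | No event. If the TTP rule is borrowed: censored at 16 - 8 = 8 weeks |
| DOR with death counted | Event at 20 - 8 = 12 weeks |

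PFS and DOR as written disagree on whether this patient's course has ended.

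**Number of responders.** Section 7.2 rejects the null hypothesis at 11 or more responses in 33. At the target ORR of 40%, 0.40 x 33 = 13.2 responders are expected, or 0.40 x 38 = 15.2 if all 38 accrued patients contribute. The two-stage rule itself checks out: exact binomial sums give a type I error of 0.046 at 20% and power of 0.801 at 40%, in line with the stated 0.05 and 80%. A range of 11 to 15 responders is therefore a fair basis.

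**Effect on the median.** Assume constant hazards, lambda_P for progression and lambda_D for death without documented progression, and let f = lambda_D / (lambda_P + lambda_D) be the share of response-ending events that are such deaths. Then

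- median with deaths censored = ln 2 / lambda_P
- median with deaths counted = ln 2 / (lambda_P + lambda_D)
- ratio = (lambda_P + lambda_D) / lambda_P = 1/(1-f)

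| f (assumed) | 1/(1-f) | Inflation |
|---|---|---|
| 0 | 1.00 | none |
| 5% | 1.053 | +5% |
| 10% | 1.111 | +11% |
| 20% | 1.250 | +25% |

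The formula takes censoring at the time of death. Censoring at an earlier scan also removes some follow-up time, so the ratio would then be somewhat smaller.

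**What one or two deaths mean.** If every responder's response has ended, one death in 15 gives f = 1/15 = 7% (ratio 15/14, +7%), and two deaths in 11 give f = 2/11 = 18% (ratio 11/9, +22%). If some responses are ongoing there are fewer events and f is larger: two deaths among 8 events give f = 2/8 = 25% (ratio 1/0.75, +33%).

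**How likely at least one such death is.** With R ended responses the chance is 1 - (1-f)^R. For R = 11 and 13 this is 43% and 49% at f = 5%, 69% and 75% at f = 10%, and 91% and 95% at f = 20%.

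**A Kaplan-Meier median moves in steps.** Take 13 responders whose responses end at 2, 4, ..., 26 months. With all counted as events the median is 14 months. If the third and fifth (months 6 and 10) are deaths and are censored, it is 16 months. If the deaths all fall after month 14, it stays at 14.

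**The case against.** The strongest objection is that progression-only is a convention the protocol uses on purpose. TTP has the same event as DOR, with deaths explicitly censored, so the difference between DOR and PFS is not in itself a contradiction, and no passage requires DOR to follow PFS. That stands. A reader might infer that the protocol contradicts itself here; it does not. The point rests on what DOR is meant to describe and on the lack of a death-inclusive version beside it.

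Second, a reader might infer that DOR will be overstated. The documents do not support that as a fact. It requires at least one responder to die without documented progression, and it requires that death to be censored. The protocol writes that censoring rule for TTP, not for DOR. If such patients were left out of DOR instead, 1/(1-f) would not apply.

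Third, censoring details may sit in a statistical analysis plan that is not shown, so the absence of a DOR censoring rule is not in itself a fault. The event, however, is fixed in the protocol, as progression only, and that is what is criticised.

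Fourth, DOR is descriptive. It shares one of eight secondary objectives with DCR and TTR, and no hypothesis, threshold or stopping rule uses it. All deaths still count in OS, and deaths before progression count in PFS, so they are not hidden from the results. This limits the weight of the point. It does not remove it, because PFS and OS cover all patients from consent and do not show how long responders stayed in response.

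**Conclusion.** The point holds in conditional form. As written, a responder's death does not end the response. If such a death occurs and is censored as for TTP, DOR may be overstated and will disagree with PFS for that patient. If none occurs, there is no effect.

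The size cannot be derived from the documents. The illustrated 5% to 25% rests on assumed values of f from 5% to 20%, constant hazards and censoring. One or two deaths correspond to f of about 7% to 18% only if all 11 to 15 responders have an event, and to more if fewer do. With so few responders the actual Kaplan-Meier median could move by more or less than this, or not at all.

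The primary ORR test, its decision rule and the sample size are untouched. This is a definition worth correcting before analysis, not a threat to the trial's main conclusion.

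**What to change.** In section 6.2, define DOR as the time from first documented CR or PR to radiographic progression per RECIST 1.1 or death from any cause, whichever is first. Censor responders alive without progression at their last radiographic assessment, as for PFS. Adding DOR to the outcomes named for Kaplan-Meier estimation in section 7.1 would make the method explicit.

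The cost is one sentence, or two with the section 7.1 addition. No new data are needed, since deaths are recorded under section 6.3 and OS already requires the date of death. The downside is that the reported DOR may be slightly shorter. A death after scans have stopped for alternate therapy would count as an event, as it does under the current PFS wording; if the analysis plan treats that case differently, the same rule should apply to both endpoints.
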